## 3.4 Analysis Populations

### 3.4.1 Intent-to-Treat (ITT) Population

The Intent-to-Treat Population will include all randomized subjects.

### 3.4.2 Modified Intent-to-Treat (MITT) Population

The Modified Intent-to-Treat (MITT) Population will include all randomized subjects who receive at least 1 dose of study drug.

### 3.4.3 Per-Protocol (PP) Population

The Per-Protocol (PP) Population will include all subjects in the MITT Population without major protocol violations and do not meet any of the following criteria:

- Withdrawal from the study or study drug before completion of Day 14
- Did not meet all inclusion and exclusion criteria

- Poor study drug compliance over the entire treatment period or leading up to Day 14
- Rescue medication use beyond protocol-specified allowance
- Serious or severe adverse event related to study medication
- Missing valid GEBT results for either baseline or Day 14 at any pre- or post-meal timepoint.

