#### **6.4 Baseline Gastric Emptying Breath Test Visit (Days -10 to -3)**

Baseline GEBT will be performed between Days -10 and -3 after a minimum 14-day washout from motility agents.

The following procedures will be performed at the Baseline GEBT Visit (Days -10 to -3):

- Assess fasting blood glucose before gastric emptying assessments to ensure a blood glucose of  $\leq 275$  mg/dL.

■ [REDACTED]

- Obtain breath samples for GEBT twice prior to consumption of a standardized,  $^{13}\text{C}$ -enriched meal per the study manual and then at 45, 90, 120, 150, 180, and 240 minutes after meal consumption after an 8-hour fast.
- Record prior medications.
- Obtain vital signs (including heart rate, blood pressure, respiration rate, and temperature) while subject is sitting after a minimum 5-minute rest.

■ [REDACTED]

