#### 6.6.9 Day 14 (±2 Days)

The following procedures will be performed on Day 14 (±2 days):

- Record concomitant medications and adverse events.
- Collect urine samples for the following:
  - Urinalysis.
  - Urine drug screen.
- Perform complete physical examination (general appearance, skin, head, eyes, ears, mouth, oropharynx, neck, heart, lungs, abdomen, extremities, and neuromuscular system).
- Obtain vital signs (including heart rate, blood pressure, respiration rate, and temperature) while the subject is sitting after a minimum 5-minute rest.

- Perform 12-lead ECG [REDACTED]  
[REDACTED]  
[REDACTED]

Note: 12-lead ECGs should be performed in triplicate approximately 1 minute apart after the subject has been resting in the supine position for at least 10 minutes. ECGs performed after the morning dose should be completed  $\pm 15$  minutes from the specified timepoints [REDACTED]  
[REDACTED]

Note: 12-lead ECGs will be printed and will be interpreted as soon as possible by the Investigator. A digital recording of each ECG will be submitted to a central reviewer.

- Fasting blood glucose will be assessed before study drug administration and gastric emptying assessments to ensure a blood glucose of  $\leq 275$  mg/dL.

[REDACTED]  
[REDACTED]  
[REDACTED]  
[REDACTED]

- Collect blood samples for the following:
  - Chemistry, hematology, coagulation, and prolactin. Sample collected predose.
  - Serum pregnancy test (only for females who are not surgically sterile or postmenopausal for at least 1 year [with confirmed FSH in postmenopausal range at the Screening Visit]).

q [REDACTED]

[REDACTED]  
[REDACTED]  
[REDACTED]

[REDACTED]  
[REDACTED]

[REDACTED]  
[REDACTED]  
[REDACTED]

[REDACTED]  
[REDACTED]  
[REDACTED]

- Obtain breath samples for GEBT (twice prior to consumption of a standardized,  $^{13}\text{C}$ -enriched meal and then at 45, 90, 120, 150, 180, and 240 minutes after meal consumption).
- Administer study drug (all subjects will take a dose of blinded study drug [CIN-102 or placebo capsules] orally at [REDACTED] AM [REDACTED]  
[REDACTED]

Study drug will be administered and the subject will consume the GEBT meal beginning 30 minutes postdose. The subject will fast for 4 hours after the completion of the GEBT meal.

- Perform study drug accountability and collect unused study drug.

#### 6.6.10 Day 15

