### 8.1.3 Assessment of Adverse Events by the Investigator

The Investigator will assess the severity (intensity) of all adverse events (serious and non-serious) and will be graded using the CTCAE Version 5.0 criteria as shown in Table 1. The Investigator will also categorize each adverse event as to its potential relationship to study drug using the categories of yes or no.

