## 9 STATISTICS

## 9.1 Analysis Populations

The Intent-to-Treat Population will include all randomized subjects.

The Modified Intent-to-Treat (MITT) Population will include all randomized subjects who receive at least 1 dose of study drug.

The Per-Protocol (PP) Population will include all subjects in the MITT Population without major protocol violations. Reasons for excluding subjects from the PP Population and will be described in detail in the Statistical Analysis Plan.

The PK Population will include all subjects who receive at least 1 dose of CIN-102 and have at least 1 quantifiable postdose plasma CIN-102 concentration.

The PK Evaluable Population will include subjects who receive CIN-102 and have sufficient plasma concentration data to characterize at least 1 PK parameter.

The PD Population will include all subjects who receive study drug and have at least 1 prolactin value following the start of study drug administration.

The Safety Population will consist of all randomized subjects who receive any study drug.

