### 3.5 Efficacy Assessments

The efficacy assessments will be analyzed and listed for the ITT Population. The analyses may also be repeated for other Analysis Populations (MITT or PP Population) as well as for subgroups of these Analysis Populations. Meal data recorded as part of the GEBT will also be listed for the ITT Population.

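### The SAP's Per-Protocol set excludes subjects for a drug-related serious or severe adverse event, which is a post-randomization outcome and not a protocol violation.

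*SAP*

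**What the plan says.** Protocol 9.1 gives the basis of the set: "The Per-Protocol (PP) Population will include all subjects in the MITT Population without major protocol violations". Its next sentence leaves the detailed reasons for exclusion to the SAP.

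SAP 3.4.3 keeps that basis and adds six exclusion criteria. In short, they are:

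1. leaving the study or study drug before Day 14 is complete;
2. failing an eligibility criterion;
3. poor compliance;
4. rescue use beyond the allowance;
5. "Serious or severe adverse event related to study medication";
6. "Missing valid GEBT results for either baseline or Day 14 at any pre- or post-meal timepoint".

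On how relatedness is decided, Protocol 8.1.3 says: "The Investigator will also categorize each adverse event as to its potential relationship to study drug using the categories of yes or no". Under Protocol 5.3 and SAP 2.2.5, the sponsor and all clinical personnel are blinded to treatment when that judgment is made.

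SAP 3.5 analyses efficacy on the ITT population and then adds an option: "The analyses may also be repeated for other Analysis Populations (MITT or PP Population".

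**The concern.** A PP analysis is meant to show the result among subjects who followed the protocol. Criteria 1 to 4 describe departures from it. Criterion 5 does not: a subject can take every dose, attend every visit, provide both breath tests and still be removed for having reacted to study drug.

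The study compares several doses with placebo, and Protocol 1.3 says its results will support dose selection. If related severe events are more common in one arm than another, criterion 5 filters the arms at different rates, and those left are selected partly on tolerance. If PP is then set beside ITT, the two could differ, or appear to agree, for reasons unrelated to adherence.

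Criterion 6 raises a lesser question. It removes a subject for one missing timepoint at either visit, without asking whether the breath-test endpoint can still be calculated.

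**Working it through.** **Plan's own count.** SAP 2.2.1 and 2.2.5 give three cohorts of 15 active and 5 placebo: 3 × (15 + 5) = 60, that is 45 active and 15 placebo. This matches the 60 (15 per treatment) in SAP 2.2.7. No power, effect size or SD is stated, so there is no sample-size calculation to reproduce.

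**What criterion 5 adds.** Take a subject with a related serious or severe event.

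- If the subject stops study drug or leaves before completing Day 14, criterion 1 already applies.
- If the event leads to missed doses, criterion 3 can apply.
- If it leads to rescue use beyond the allowance, criterion 4 applies.
- If none of these holds and the breath tests are complete, only criterion 5 removes the subject.

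The bullet's own effect is therefore on compliant completers.

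**Size of one exclusion.** It is 1/15 = 6.7% of a dose group. SAP 3.2 does not pool placebo across cohorts for efficacy, although Protocol 9.2 does. On the SAP's reading, one excluded placebo subject is 1/5 = 20% of a cohort's placebo group.

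**How often it could act.** The documents give no rates, so r, the chance that a subject has a related serious or severe event, is an assumption. For an arm of 15, the expected number is 15r and the chance of at least one is 1 − (1 − r)^15. Both are upper limits for criterion 5, because some of these subjects would also meet criterion 1.

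| assumed r | expected of 15 | chance of at least one |
|---|---|---|
| 2% | 0.30 | 26% |
| 5% | 0.75 | 54% |
| 10% | 1.50 | 79% |

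With an assumed 5% on active and 2% on placebo, about 45 × 0.05 = 2.25 active and 15 × 0.02 = 0.3 placebo subjects would have such an event.

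**Effect on an arm mean.** If a share q is excluded and their mean change differs by d (in SD units) from that of those kept, the PP mean differs from the full-arm mean by q × d. For one of 15, this is 0.067 × 0.5 = 0.03 SD or 0.067 × 1.0 = 0.07 SD. The values of d are assumptions, and the documents do not indicate the direction.

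**Criterion 6 (secondary).** At baseline, Protocol 6.4 says "Obtain breath samples for GEBT twice prior to consumption of a standardized" meal, "and then at 45, 90, 120, 150, 180, and 240 minutes after meal consumption": 2 + 6 samples. Protocol 6.6.9 repeats this at Day 14. The total is (2 + 6) × 2 = 16 samples, or (1 + 6) × 2 = 14 timepoints if the paired pre-meal samples count once. If each fails independently with probability p (both assumptions), the share excluded is 1 − (1 − p)^k:

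| assumed p | k = 16 | k = 14 |
|---|---|---|
| 0.5% | 7.7% | 6.8% |
| 1% | 14.9% | 13.1% |
| 2% | 27.6% | 24.6% |

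If one valid sample of each pre-meal pair were enough, about 12 samples would matter, and the shares would be 5.8%, 11.4% and 21.5%. Failures clustered within one test would lower all of these. The tables show sensitivity to assumptions and are not estimates for this trial.

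**The case against.** The strongest reply is that little depends on the PP set. ITT is the set named for efficacy, it keeps every subject at issue, and PP may never be run. The visible text plans descriptive summaries, and the sections on the Data Review Committee do not mention PP. This stands, and it limits the harm.

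The protocol also delegates the PP exclusions to the SAP, so adding criteria is not in itself a departure. That stands too. The objection is to the kind of criterion, not to the SAP's right to add one.

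A reader might infer that the bullet acts almost only on active arms and leaves placebo unselected. The documents do not support this: it applies to all arms and relatedness is judged blind. A reader might also infer that the bias grows with dose and distorts dose selection. No event rates by arm or dose are given, nothing shows that affected subjects empty differently, and Protocol 1.3 ties dose selection to the study's results, not to PP.

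The added effect may also be small. Protocol 3.3.1 and 3.3.2 suspend or cease dosing after related serious events of specified grades, and Protocol 4.4 lists serious and clinically significant events as grounds for withdrawal, which criterion 1 already covers when it comes before Day 14 is complete. What is left is mainly related severe but non-serious events in completers, whose number is unknown.

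On criterion 6, the tempting reading is that the plan discards evaluable subjects. No passage says that a test with a missing sample is evaluable. SAP 3.5.1 lists a time-weighted average first, for which a complete curve is a defensible PP requirement. In the other direction, SAP 3.5.2.1 summarizes each post-meal timepoint separately, so a subject with one gap still has usable values.

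**Conclusion.** The point holds for the adverse-event bullet. It conditions PP membership on a post-randomization outcome, and its own effect is to remove subjects who adhered. Any PP comparison can therefore lose randomized comparability, by an amount the documents do not allow to be estimated. One exclusion is 7% of a 15-subject dose group, and on the assumptions shown it would move that arm's mean by about 0.03 to 0.07 SD. ITT results are unaffected and PP is optional, so this is a modest defect worth correcting because the correction is nearly free.

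Confidence is low on the breath-sample bullet. It may drop subjects whose endpoint can still be calculated, but with no sample-failure rate and no minimum sample count in the documents, its size is unknown.

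**What to change.** In SAP 3.4.3, delete the adverse-event bullet. Add a sentence that PP membership will be decided and documented before unblinding; the visible SAP text does not say when this is done.

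Optionally, replace the breath-sample bullet with a criterion that the analysed breath-test endpoint cannot be calculated at baseline or at Day 14, and have the sponsor state the minimum samples needed. The wording should cover whichever endpoint is analysed, the time-weighted average as well as T1/2, so that subjects do not enter PP without the value being summarized.

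The cost is SAP wording only. The PP set may grow slightly. Selection through the early-withdrawal bullet remains, because subjects who stop for an adverse event before completing Day 14 are still excluded, so PP results would still need to be read beside ITT.

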#### 3.4.4 PK Population

The PK Population will include all subjects who receive at least 1 dose of CIN-102 and have at least 1 quantifiable postdose plasma CIN-102 concentration.

#### 3.4.5 PK Evaluable Population

The PK Evaluable Population will include subjects who receive CIN-102 and have sufficient plasma concentration data to characterize at least 1 PK parameter.

#### 3.4.6 PD Evaluable Population

The PD Population will include all subjects who receive study drug and have at least 1 prolactin value following the start of study drug administration.

#### 3.4.7 Safety Population

The Safety Population will consist of all randomized subjects who receive any study drug.

#### 3.4.8 Subgroup Analyses

In addition to the analysis populations listed, efficacy, PK, and/or safety analyses may be repeated for certain subgroups. These may include, but are not limited to:

- Screening GEBT  $T_{1/2}$  scores of  $<110$  and  $\geq 110$
- Diabetic and idiopathic gastroparesis types
- Diabetic subjects: with and without neuropathy

### 3.5 Efficacy Assessments

The efficacy assessments will be analyzed and listed for the ITT Population. The analyses may also be repeated for other Analysis Populations (MITT or PP Population) as well as for subgroups of these Analysis Populations. Meal data recorded as part of the GEBT will also be listed for the ITT Population.

#### 3.5.1 Primary Efficacy Assessments

Gastric empty time (time-weighted average,  $1000 \times$  percent  $^{13}\text{C}$  dose excreted per minute, and  $T_{1/2}$ ) will be determined by GEBT at Day 14 ( $\pm 2$  days). The value, change from baseline, and percent change from baseline (gathered on Days -10 to -3) in gastric emptying as measured by GEBT to Day 14 ( $\pm 2$  days) will be summarized by visit and treatment group.

GEBT results are reported using kPCD, a metric which expresses a subject's  $^{13}\text{CO}_2$  excretion rate at each measurement time as defined below.

- kPCD: a mathematical expression of a test subject's  $^{13}\text{CO}_2$  excretion rate (per minute, denoted as  $\text{min}^{-1}$ ) at any measurement time  $t$  relative to the dose of carbon-13 contained in the test meal.

$$\text{kPCD}(t) = 1,000 \times [\text{percent dose } ^{13}\text{C} \text{ excreted as } ^{13}\text{CO}_2 \text{ per minute (min}^{-1}\text{) at time } t]$$

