### 1.3 Study Rationale

To date, the PK, pharmacodynamics (PD; based on increases in prolactin), and safety of CIN-102 have been evaluated in a SAD study and a MAD study in healthy subjects. The current study is the first study in subjects with gastroparesis. As such, this study is intended to evaluate the effect of CIN-102 on gastric emptying in subjects with idiopathic or diabetic gastroparesis over a range of doses. The safety, PK, and effect of CIN-102 on symptoms of gastroparesis in these subjects will also be assessed in this proof of concept study. The results of this study will be used to support dose selection for future studies.

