### 5.3 Randomization and Blinding

Subjects who have completed the Screening Visit and meet all of the inclusion, none of the exclusion criteria, and all of the additional criteria based on randomization procedures, including safety laboratory tests (see [Section 6.5](#)), will be randomized into the study. Randomization will occur on Day 1. Randomization assignments will be provided by [REDACTED] (IRT). Following randomization, study drug will be dispensed in a double-blind manner on Day 1. The Sponsor and all clinical personnel will be blinded to the treatment group for each subject. Subjects will also be blinded to the treatment they receive.

Subjects will be stratified at randomization based on their etiology for gastroparesis (ie, diabetic gastroparesis versus idiopathic gastroparesis).

Bioanalytical staff involved in analysis of PK samples will be unblinded to treatment either via receipt of the randomization code to allow for analysis of samples from subjects receiving CIN-102 only (and possibly limited analysis of samples from subjects receiving placebo), or by the nature of the results of sample analysis. The PK data will be de-identified before being provided to any other individuals, including those involved in calculating PK parameters and associated descriptive statistics, performing any modelling or simulations, and/or plotting PK data, in order to maintain blinding.

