## 1 INTRODUCTION

This statistical analysis plan (SAP) provides a detailed, technical elaboration of the statistical analyses of safety, efficacy, pharmacokinetics (PK), and dose response of oral CIN-102 in adults with idiopathic and diabetic gastroparesis as described in the study original protocol (dated 19 May 2019), Version 2.0 amendment 1 (dated 15 Aug 2019), and version 3.0 amendment 2 (dated 13 Nov 2019). Specifications for tables, listings, and figures are contained in a separate document.

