#### 2.2.5 Randomization and Blinding

Subjects who have completed the Screening Visit and meet all of the inclusion, none of the exclusion criteria, and all of the additional criteria based on randomization procedures, including safety laboratory tests (see Section 6.5), will be randomized into the study. Randomization will occur on Day 1 and randomized treatment assignments will be provided by Medpace Interactive Response Technology (IRT). Subjects will be randomized to either CIN-102 or placebo in a 3:1 ratio in each cohort.

The study will begin by randomizing subjects in Cohort 1 to either CIN-102 [REDACTED] BID or placebo BID such that 15 subjects receive CIN-102 and 5 subjects receive placebo. Currently planned dose levels for Cohorts 2 and 3 are [REDACTED] QD and [REDACTED] BID, respectively, with 15 subjects receiving study drug and 5 subjects receiving placebo in each cohort.

For Cohort 1, subjects will be stratified at randomization based on their etiology for gastroparesis (i.e., diabetic gastroparesis versus idiopathic gastroparesis). For Cohorts 2 and 3, subjects will be stratified by screening GEBT  $T_{1/2}$  result ( $<110$  versus  $\geq 110$ ).

Following randomization, study drug will be dispensed in a double-blind manner on Day 1. The Sponsor and all clinical personnel will be blinded to the treatment group for each subject. Subjects will also be blinded to the treatment they receive.

Bioanalytical staff involved in analysis of PK samples will be unblinded to treatment either via receipt of the randomization code to allow for analysis of samples from subjects receiving CIN-102 only (and possibly limited analysis of samples from subjects receiving placebo), or by the nature

of the results of sample analysis. The PK data will be de-identified before being provided to any other individuals, including those involved in calculating PK parameters and associated descriptive statistics, performing any modelling or simulations, and/or plotting PK data, in order to maintain blinding.

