##### 3.1.4 Summary Statistics

Categorical data will generally be summarized with counts and percentages of subjects. The denominator used for the percentage calculation will be clearly defined. Continuous data will generally be summarized with descriptive statistics including n (number of non-missing values), mean, median, standard deviation, minimum, and maximum.

Geometric mean (GM) and GM CV will also be provided for PK concentrations and parameters. The subjects with a 0 (zero) value will be excluded from the calculation of GM and GM CV.

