### 3.5.2 Secondary Efficacy Assessments

#### 3.5.2.1 GEBT $T_{1/2}$ and Timepoints

The value, change from baseline, and percent change from baseline in gastric emptying BT  $T_{1/2}$  as measured by GEBT at Day 14 ( $\pm 2$  days) will be summarized by treatment group. The value and time-matched (to baseline visit) change from baseline and percent change from baseline of the GEBT results for each post-meal timepoint will also be summarized by treatment group.

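### The SAP tabulates gastric emptying by treatment group but specifies no difference from placebo, confidence interval, baseline adjustment or dose-response estimate

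*SAP*

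**What the plan says.** SAP 3.5.1 names three GEBT metrics: a time-weighted average, the scaled 13C excretion rate (kPCD) and T1/2. For these it lists "The value, change from baseline, and percent change from baseline (gathered on Days -10 to -3) in gastric emptying as measured by GEBT", and says that the Day 14 results "will be summarized by visit and treatment group". SAP 3.5.2.1 treats BT T1/2, listed as a secondary variable, in the same way and adds: "The value and time-matched (to baseline visit) change from baseline and percent change from baseline of the GEBT results for each post-meal timepoint". SAP 3.1.4 defines the summary: "Continuous data will generally be summarized with descriptive statistics including n (number of non-missing values), mean, median, standard deviation, minimum, and maximum".

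The stated scope is wider. SAP section 1 says the plan elaborates "the statistical analyses of safety, efficacy, pharmacokinetics (PK), and dose response of oral CIN-102", and protocol 1.3 says "The results of this study will be used to support dose selection for future studies".

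The two documents give different stratification schemes. Protocol 5.3 says: "Subjects will be stratified at randomization based on their etiology for gastroparesis (ie, diabetic gastroparesis versus idiopathic gastroparesis"), with no limit by cohort. SAP 2.2.5 keeps etiology for Cohort 1 only and then says: "For Cohorts 2 and 3, subjects will be stratified by screening GEBT" T1/2, below 110 versus 110 or more. In the analysis, both factors return only in SAP 3.4.8, as subgroups in which analyses may be repeated.

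Protocol 4.3 requires a GEBT T1/2 above 80 minutes within 10 days before the first dose, and protocol 6.5 describes the baseline GEBT as confirming eligibility. One test therefore serves as both entry criterion and baseline.

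**The concern.** A randomized, placebo-controlled trial with dose response in its title would, as the SAP reads, be reported as four or more columns of means and SDs. Three things are then left open.

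- **Effect and uncertainty.** No estimate of dose minus placebo is defined and no interval is attached. Whoever selects the next dose cannot see how imprecise a comparison with 15, or 5, placebo subjects is. The choice among value, change and percent change, on several metrics, is left until the data are in.
- **Within-arm change.** Subjects enter because their baseline T1/2 was high, so T1/2 will tend to fall on retest in every arm, treated or not. Read within one arm, that fall looks like improvement.
- **Dose response.** Nothing is estimated. SAP 3.7 offers only exposure scatterplots that may be made.

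**Working it through.** **1. The plan's own figure.** Three cohorts of 15 active + 5 placebo give 3 × 20 = 60 subjects, with 3 × 5 = 15 on placebo. This agrees with the stated 60, 15 per treatment. The documents state no alpha, power, SD or effect size, so there is no power to reproduce. Every SD, mean and correlation below is an assumption.

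**2. Regression to the mean in T1/2.** Take a normal screened population with mean μ and SD σ, baseline/Day 14 correlation ρ and no drug effect. Selection at 80 minutes gives an expected fall of (1−ρ) × σ × m, where m = φ(c)/(1−Φ(c)) and c = (80−μ)/σ.

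- Largest (μ 75, σ 30, ρ 0.5): c = 0.167, m = 0.907, fall = 0.5 × 30 × 0.907 = 13.6 min.
- Smallest (μ 100, σ 25, ρ 0.8): c = −0.8, m = 0.368, fall = 0.2 × 25 × 0.368 = 1.8 min.

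In simulation (μ 90, σ 30), an ineffective arm of 15 showed a within-arm shortening with two-sided p<0.05 in 21%, 14% and 7% of runs at ρ 0.5, 0.7 and 0.9, against a nominal 2.5% in that direction. The expected shift is the same in every randomized arm, so dose minus placebo removes it.

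**3. Precision of the missing contrast**, in SDs of the analysed variable:

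| Comparison | SE = √(1/n₁+1/n₂) | t (df) | 95% half-width |
|---|---|---|---|
| 15 v 15 (placebo pooled, protocol 9.2) | 0.365 | 2.048 (28) | 0.75 |
| 15 v 5 (not pooled, SAP 3.2) | 0.516 | 2.101 (18) | 1.08 |

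A fixed cohort term matters here. Each cohort holds one dose and its own placebo, so four treatments and three cohorts need 1 + 3 + 2 = 6 parameters for 6 cell means. Each dose-minus-placebo estimate is then the within-cohort 15 v 5 difference (SE 0.516). Pooling then helps only the residual variance: with 60 − 6 = 54 df, t = 2.005 and the half-width is 1.04 SD.

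**4. What baseline adjustment adds.** Without selection, Var(ANCOVA)/Var(change) = (1+ρ)/2. Selection shrinks the baseline variance by k = 1 + c·m − m², and the ratio becomes (1+ρ)/[(1+ρ) + (1−ρ)k].

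- μ 100, σ 25, ρ 0.3: k = 0.571, ratio = 1.3/(1.3 + 0.7 × 0.571) = 0.76, like 31% more subjects.
- μ 75, σ 25, ρ 0.8: k = 0.322, ratio = 1.8/(1.8 + 0.2 × 0.322) = 0.97, like 4% more subjects.

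**5. A linear trend contrast.** Assume four groups of 15, equal dose spacing, pooled placebo, no cohort term, a 1-SD top-dose effect and two-sided 0.05. With weights −1.5, −0.5, 0.5, 1.5 (sum of squares 5), the contrast in units of its SE is as follows:

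- Linear response (0, 1/3, 2/3, 1): (5/3)/√(5/15) = 2.89, power 81%.
- Plateau (0, 1, 1, 1) or top dose only (0, 0, 0, 1): 1.5/√(5/15) = 2.60, power 72%.
- Pairwise top dose v 15 placebo: power 75%.

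The contrast's advantage therefore depends on the response shape. Spacing cannot be derived either, because the doses are redacted and Cohort 2 is once daily in the SAP but twice daily in the protocol.

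**The case against.** This is a Phase 2A proof-of-concept study with no formal sample-size assessment, and descriptive reporting is a legitimate choice at that stage. The SAP makes no confirmatory claim. It tabulates Day 14 values as well as change, with placebo beside the active groups, so a reader can compare by eye. All of this stands, and it limits the point to missing estimates. An interval needs no power claim, however, and with groups this small it is the most useful thing to report.

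A reader might infer several stronger things that the documents do not support:

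- *Efficacy will be judged from within-arm change, or selection biases the comparison with placebo.* The SAP never says the first, and randomization makes the shift equal across arms in expectation.
- *No comparison was ever planned.* Protocol 9.2.1 is not legible and the synopsis analysis text is partly redacted, so the point is confined to the SAP.
- *The strata are ignored.* They appear as optional subgroups. What is absent is adjustment.
- *Exposure-response is absent.* Protocol 9.2.1.5 plans an attempt at correlation and SAP 3.7 allows plots. Neither defines an estimate.
- *All GEBT metrics carry the same regression to the mean.* Selection is on T1/2; the others are affected only through their correlation with it.

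**Conclusion.** The point holds for the readable SAP and should be fixed, though it does not invalidate the trial. SAP 3.5.1, 3.5.2.1 and 3.1.4 provide arm-level summaries only, which falls short of the SAP's own scope and of the protocol's use of the results for dose selection.

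The main loss is a defined placebo contrast with its interval: about ±0.75 SD with 15 pooled placebo subjects and ±1.08 SD with 5. Within-arm T1/2 change carries roughly 2-14 minutes of regression to the mean under the assumptions in step 2. Baseline adjustment is worth about 4%-31% more subjects for assumed correlations of 0.3-0.8, once truncation at 80 minutes is counted. It would be tempting to quote the untruncated formula, or a power advantage for a trend test. The first ignores the entry criterion, and the second holds only for favourable response shapes.

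The stratification conflict between protocol 5.3 and SAP 2.2.5 is textual and needs no assumption.

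**What to change.** - **Model.** In SAP 3.5.1 and 3.5.2.1, add an ANCOVA of the Day 14 value for each listed GEBT metric, including BT T1/2 (log scale if skewed). Covariates: treatment, continuous baseline of the same metric, baseline T1/2 (the same covariate when T1/2 is analysed), etiology and cohort. Report each dose minus placebo with a 95% interval, labelled as estimation without a confirmatory claim. Fitting every listed metric leaves BT T1/2 in its secondary place.
- **Placebo group.** Reconcile SAP 3.2 (not pooled for efficacy) with protocol 9.2 (pooled). If pooled, keep the cohort term, because cohorts may run serially, and state that the contrast then rests on within-cohort placebo (step 3). A pooled analysis without the term could be shown as a sensitivity analysis, with its assumption of no drift between cohorts stated.
- **Dose response.** Add one supportive contrast on total daily dose or AUC, without quoting a power advantage.
- **Strata.** Reconcile protocol 5.3 and SAP 2.2.5 to the scheme the IRT actually used. Continuous baseline T1/2 and etiology cover both schemes, provided the screening GEBT in the SAP is the Day -10 to -3 test, the only pre-dose GEBT in the schedule.

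The cost is SAP wording and programming. The covariates are already collected, so no subjects, visits or assays are added.
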